**Specific Aims:** Aim 1 will assess functional performance associated with use and wear of three different commercially available MPKs and one research grade powered knee in 17 individuals with TFA. Aim 2 will assess subjective patient reported preferences associated with use of the same four prosthetic knees along with collection of subject specific anthropomorphic characteristics that may correlate with MPK choice. Aim 3 will generate the clinical decision algorithm for MPK selection.

**Study Design:** Our study revolves around clinical tests and outcomes measures to evaluate the biomechanical performance and patient reported outcomes of three different commercially available MPKs and a single research grade powered knee in individuals with a TFA. We will test the hypothesis that differences will emerge between individuals when wearing the different knees and that these differences will be predictable. Subjects will ambulate over various terrains to simulate community ambulation with each MPK (Aim 1) allowing for assessment of the functional performance of each MPK. Through collection of individual anthropomorphic data and psychometric outcomes measures (Aim 2), we predict individual preferences and biomechanical improvements will emerge between the various MPKs

allowing for the generation of a clinical decision algorithm for MPKs (Aim 3).

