During the first visit, fitting and tuning will be no longer than 4 hours. Participants may end the visit at any time without penalty, or choose not to return for additional visits. If the participant agrees to continue the study subsequent visits will be scheduled at their convenience and pending availability of the prosthetic knee joints. During these subsequent visits, testing will last between 2-6 hours based on participant comfort.

Participants will be asked to attend at least 5 sessions in order to compare the effectiveness of the different prosthetic knees. However, each participant will maintain the right to discontinue their involvement for future sessions. Depending on the progress of the tests, participants may be involved in sessions ranging over the course of a few months.

The results of the study will be in the form of device performance and participant feedback. Sensor data will record the movement parameters of the subject. This includes mechanical instruments on the device and biomechanical instruments attached to both the device and the human subjects. These instruments will give information about the kinematics (movement), kinetics (force), muscle activity, step count, heart rate and metabolics of the user. This allows for the effectiveness of the design strategy to be assessed. The participants will also give feedback in the form of verbal conversation. This verbal feedback will deal with the comfort, convenience and preferences of the devices and controllers.

This study will use statistical analysis to compare between different intent recognition systems. We will use intent recognition accuracy as the primary metric to compare statistical differences across conditions. We will compare biomechanics between the powered device and a passive prosthesis. Typically, ANOVA tests are used with repeated measures to compare across multiple conditions.

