### Statistical & data analysis plan

A repeated measures ANOVA with within factor MPK will be used to assess differences across treatment for Aims 1 and 2, provided assumptions are met. In the event of missing data or violation, a linear mixed models procedure, which does not assume compound symmetry, will be considered. Bonferroni-Holmes correction will be made to control for family-wise error rate. Samples size calculations are outlined below. Estimated effect size was calculated using Cohen's d for within factor designs [71], assuming a correlation among repeated measures of 0.5. Effect sizes were then converted to Cohen's f for sample size estimations using G\*Power. [72] **Aim 1: Comparison of clinical outcome measures on MPKs.** A Borg RPE of 2 (pooled SD= 2) was deemed clinically relevant for this study, resulting in an effect size of 1. Gait variability index effect size was based upon minimally detectable change (MDC) cited in [73]. An MDC of 8 and hypothesized pooled SD of 6, produced an effect size of 1.3. These data indicate a sample size of approximately 9 will achieve 90% power. The sample size proposed in this study (N=12) should ensure adequate power, even in the event of attrition or slightly higher variability. **Aim 2: Patient reported outcomes.** Resnik & Borgia (2011) have suggested a MDC of 10.3 (90% CI) for OPUS lower limb function.[61] Effect size for this study was calculated using MDC of 10 and a pooled SD of 7.7, assuming higher variability than previously reported SD's for upper

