extremity [73]. This resulted in a Cohen's D of 1.3. Resnik & Borgia (2011) also reported PEQ subscale MDC's which ranged from 0.8-1.4 with Std errors of 0.3-0.6.[61] Based upon an MDC of 1.1 and SD of 1.25, Cohen's d would be 0.88. The sample size of 9 corresponds to 80% power. The SF36V will be used as an additional measure of health related QOL but due to high variability reported in the literature (from the inclusion of both mental and physical function scales)[61], this measure will not be powered by this preliminary study. Instead, this measure will be used to look for clinical trends in the data and aid in potential direction for the future larger study outlined in our transition plan. **Aim 3: Clinical Decision Algorithm.** The creation of the clinical decision algorithm for personalizing the MPK prescription to an individual is an exploratory, informative analysis that is constrained by population size and resources. Repeated sampling is employed to increase the information gained while attempting to minimize within subject variability and provide better examination of relationships. It is expected that in initial development, large effect sizes will be detected which play a critical role in the satisfaction with the use of prosthetic devices. To be valuable to clinical decision making, it is imperative that identification of this causal mechanism include factors other than solely clinical measurements. In addition, proximal outcomes, based on existing knowledge, will supplement the model. This process will lay the groundwork for the decision tree to be refined over time as the sample can be increased. There are a number of models that can be used for this aim (Bayesian approaches, linear discriminant analysis for repeated measures, etc.) which do not require as large a sample size for estimation procedures. The choice of model will be determined based on the underlying data structure by our co-I biostatistician, [name].

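### The only outcome called primary, intent recognition accuracy, does not belong to the four-knee comparison, and none of the four powered outcomes is called primary

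*Combined protocol and SAP*

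**What the plan says.** The last paragraph of section 3, just before the statistical plan, states: "This study will use statistical analysis to compare between different intent recognition systems". It continues: "We will use intent recognition accuracy as the primary metric to compare statistical differences across conditions". The next sentence adds a biomechanical comparison of the powered device with a passive prosthesis.

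The rest of the document describes a different comparison. Aim 1 in section 1 concerns "three different commercially available MPKs and one research grade powered knee in 17 individuals with TFA", and Aim 2 takes patient-reported preferences on the same four knees. The Statistical & data analysis plan says: "A repeated measures ANOVA with within factor MPK will be used to assess differences across treatment for Aims 1 and 2". It bases its power on Borg RPE and GVI for Aim 1 and on OPUS and PEQ for Aim 2. It states that the SF36V is not powered and that Aim 3 is exploratory. It calls no outcome primary.

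On error control the plan says: "Bonferroni-Holmes correction will be made to control for family-wise error rate". It gives neither alpha nor the set of tests covered. On size it says for Aim 1: "These data indicate a sample size of approximately 9 will achieve 90% power", and for Aim 2: "The sample size of 9 corresponds to 80% power".

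**The concern.** The protocol gives two incompatible accounts of what is compared and on which outcome. Under one, the condition is an intent recognition system and the outcome is its accuracy. Under the other, the condition is the knee and the outcomes are function, exertion and patient report. Only the first account uses the word primary, and only the second has procedures, a model and power behind it.

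The consequence is for the credibility of the main result. The study collects many measures per knee: gait mat variables, the 2-minute walk, exertion, physiological cost, ramp and stair biomechanics, beam walking and five questionnaires or surveys. If the declared primary is set aside as unusable, nothing says which of the others carries the conclusion, and that choice could be made once the results are known.

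**Working it through.** **1. The two accounts side by side**

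| Item | Last paragraph of section 3 | Aims, numbered steps, analysis plan |
|---|---|---|
| Conditions compared | Intent recognition systems | Three commercial MPKs and one powered knee |
| Model factor | Not named beyond conditions | MPK, within participant |
| Outcome | Intent recognition accuracy | Borg RPE, GVI, OPUS and PEQ are powered |
| Called primary? | Yes | None |
| Definition, collection step, effect size | None given | Given for all four, except that the PEQ score is not specified |

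Intent recognition accuracy appears in 0 of 3 aims, 0 of 10 numbered steps and 0 of 4 power inputs. Section 3 does allow EMG, IMUs and instruments on the device, but it derives no accuracy score from them and varies no recognition system.

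**2. What the sample size rests on**

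Inputs from the plan are the standardised differences and a correlation of 0.5 among repeated measures:

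- Borg RPE: d = 2/2 = 1.00
- GVI: d = 8/6 = 1.33 (the plan prints 1.3)
- OPUS: d = 10/7.7 = 1.30
- PEQ: d = 1.1/1.25 = 0.88

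Assumptions not in the plan are alpha = 0.05, sphericity, and the conversion f = d/2 (knees split two and two at the extremes).

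The test is a one-group repeated measures ANOVA with m = 4 knees. The noncentrality is lambda = f² × N × m / (1 − 0.5), with 3 and 3(N − 1) degrees of freedom.

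Reproducing the plan at N = 9 (3 and 24 df, critical F = 3.01):

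- Borg RPE: lambda = 0.50² × 9 × 4 / 0.5 = 18.0; power 92%
- PEQ: lambda = 0.44² × 9 × 4 / 0.5 = 13.9; power 83%

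At N = 8 the same formula gives 88% and 77%, so 9 is the smallest N meeting the stated 90% and 80%. Both stated values reproduce. The sample size therefore rests wholly on the four knee outcomes.

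**3. Does the promised Holm correction undo the stated power?**

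If Holm covers the four omnibus tests, its first threshold is 0.05/4 = 0.0125. With the same f = d/2:

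| N | lambda, Borg RPE | Power, Borg RPE | lambda, PEQ | Power, PEQ |
|---|---|---|---|---|
| 9 | 18.0 | 78% | 13.9 | 63% |
| 12 | 24.0 | 93% | 18.6 | 83% |
| 17 | 34.0 | 99% | 26.3 | 96% |

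GVI and OPUS are at about 97% or more in every row. These are first-step lower bounds, because Holm relaxes after each rejection. N = 9 is not the enrolment figure: the plan proposes 12 and the aims give 17. At either, the stated 90% and 80% hold.

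**4. Are the Aim 2 outcomes collected for every knee?**

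OPUS and PEQ are administered in step 9, which refers to each device. Step 10 then asks for steps 4 to 8 to be repeated for the remaining knees, which leaves out step 9. Repetition is probably intended, but the two steps disagree.

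**The case against.** The strongest reply is that the headed analysis plan can be run as it stands. It names the factor, the model, a mixed-model fallback and a family-wise correction. It separates powered outcomes from the SF36V, and it describes the work as preliminary. On that view the paragraph in section 3 is stray text, and insisting on a formally labelled primary in a small crossover is partly preference.

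Much of this stands. The plan is workable, and the powered set together with the Holm commitment narrows the room for choosing a headline result. It does not close it. The Holm family is undefined, four outcomes have equal standing, and the PEQ has several subscales with none specified. Nor does the plan withdraw the statement in section 3, so the conflict over the primary remains.

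A reader might infer three stronger things, none of which the documents support:

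- **That the named primary metric will have no data at all.** EMG, IMU and on-device sensor data may be collected. What can be said is that the metric is not defined, scheduled or powered.
- **That the study is underpowered once Holm is applied.** The check above shows otherwise at N = 12 and N = 17. Low figures do arise with f = d/√8 (PEQ 44% and 67% at 0.0125) or with a single pairwise contrast at 0.05/6 (PEQ 47% and 72%). But f = d/√8 does not reproduce the plan's N of 9, and the plan never mentions pairwise contrasts. The unstated alpha and Holm family are missing detail, not evidence of low power.
- **That the sentences were carried over from another protocol.** Section 11 mentions a separate, related protocol for the powered knee, so this is plausible, but the documents do not say it.

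**Conclusion.** The contradiction is real and should be corrected before any analysis. The one metric declared primary does not belong to the comparison that the aims, procedures and analysis plan describe, and none of the four powered outcomes takes its place. The finding is textual and depends on no disputed number. It is limited to the available text, since the front matter could not be checked.

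The plan's power statements are not in error on this point. That conclusion assumes alpha = 0.05, f = d/2, sphericity and Holm over four omnibus tests, and it applies to N = 12 or 17. The difference between those two enrolment figures is a separate matter.

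**What to change.** Amend the whole closing paragraph of section 3 so that it agrees with the aims and the analysis plan:

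1. Delete the two intent recognition sentences. If that outcome is truly intended, define it, schedule its collection and power it.
2. Reconcile the sentence on the powered device and a passive prosthesis with the four-knee comparison, saying which knees it refers to.
3. Name as primary one or more outcomes the plan already powers, for example GVI and/or Borg RPE for Aim 1, and OPUS and/or one specified PEQ score for Aim 2. Label the remaining measures secondary or exploratory.
4. Reconcile step 10 with step 9 so that OPUS and PEQ are recorded for every knee.

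As lower-priority detail in the same edit, state alpha and which tests Holm covers.

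The cost is small: a wording amendment with no extra participants, and no new data if step 9 was always meant to be repeated for each knee. What the investigators give up is freedom to choose the headline outcome later. If the intent recognition outcome is kept, the cost is larger, because the documents give no definition, effect size or SD from which to power it.

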### Statistical & data analysis plan

A repeated measures ANOVA with within factor MPK will be used to assess differences across treatment for Aims 1 and 2, provided assumptions are met. In the event of missing data or violation, a linear mixed models procedure, which does not assume compound symmetry, will be considered. Bonferroni-Holmes correction will be made to control for family-wise error rate. Samples size calculations are outlined below. Estimated effect size was calculated using Cohen's d for within factor designs [71], assuming a correlation among repeated measures of 0.5. Effect sizes were then converted to Cohen's f for sample size estimations using G\*Power. [72] **Aim 1: Comparison of clinical outcome measures on MPKs.** A Borg RPE of 2 (pooled SD= 2) was deemed clinically relevant for this study, resulting in an effect size of 1. Gait variability index effect size was based upon minimally detectable change (MDC) cited in [73]. An MDC of 8 and hypothesized pooled SD of 6, produced an effect size of 1.3. These data indicate a sample size of approximately 9 will achieve 90% power. The sample size proposed in this study (N=12) should ensure adequate power, even in the event of attrition or slightly higher variability. **Aim 2: Patient reported outcomes.** Resnik & Borgia (2011) have suggested a MDC of 10.3 (90% CI) for OPUS lower limb function.[61] Effect size for this study was calculated using MDC of 10 and a pooled SD of 7.7, assuming higher variability than previously reported SD's for upper

extremity [73]. This resulted in a Cohen's D of 1.3. Resnik & Borgia (2011) also reported PEQ subscale MDC's which ranged from 0.8-1.4 with Std errors of 0.3-0.6.[61] Based upon an MDC of 1.1 and SD of 1.25, Cohen's d would be 0.88. The sample size of 9 corresponds to 80% power. The SF36V will be used as an additional measure of health related QOL but due to high variability reported in the literature (from the inclusion of both mental and physical function scales)[61], this measure will not be powered by this preliminary study. Instead, this measure will be used to look for clinical trends in the data and aid in potential direction for the future larger study outlined in our transition plan. **Aim 3: Clinical Decision Algorithm.** The creation of the clinical decision algorithm for personalizing the MPK prescription to an individual is an exploratory, informative analysis that is constrained by population size and resources. Repeated sampling is employed to increase the information gained while attempting to minimize within subject variability and provide better examination of relationships. It is expected that in initial development, large effect sizes will be detected which play a critical role in the satisfaction with the use of prosthetic devices. To be valuable to clinical decision making, it is imperative that identification of this causal mechanism include factors other than solely clinical measurements. In addition, proximal outcomes, based on existing knowledge, will supplement the model. This process will lay the groundwork for the decision tree to be refined over time as the sample can be increased. There are a number of models that can be used for this aim (Bayesian approaches, linear discriminant analysis for repeated measures, etc.) which do not require as large a sample size for estimation procedures. The choice of model will be determined based on the underlying data structure by our co-I biostatistician, [name].

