## **Protocol for Personalizing MPK Prescription for Individuals With Transfemoral Amputation**

### **1. Study Aim, Background and Design**

**Background:** Published data shows approximately 35% of service members who sustain an amputation have it occur at the transfemoral level. Significant evidence indicates microprocessor knees (MPKs) have numerous benefits over non-MPKs for individuals with transfemoral amputation (TFA) including improved gait, safety, comfort, confidence, reduced falls, balance, patient satisfaction and reduced energy expenditure, greater ease in negotiating varying terrains, improvements in multi-tasking and cost effectiveness, such that MPK technology should be considered current state-of-the-art in TFA prosthesis prescription. However, studies which currently exist on MPK technology tend to lump the various knees together as a group rather than teasing out differences between the individual MPK technology and what types of patients are best suited for each. Therefore, a gap exists in clinical knowledge forcing clinicians to choose componentry based on reimbursement or their past experiences with an MPK, rather than detailed evidence supporting the use of one MPK for a certain individual. In this proposal, we will assess the biomechanical function and patient reported outcomes of each subject while they are using three commercially available MPKs and a research grade powered knee, addressing the FY20 OPORP Focus Areas “Prosthetic Device Function” and “Prosthetic Device Form”.

**Hypothesis/Objective:** Our *objective* is to personalize the prosthetic prescription process by creating a clinical decision algorithm for selection of an ideal MPK for an individual patient with transfemoral amputation (TFA) based on objective and patient reported data collected from that specific user. We test the *central hypothesis* that biomechanical and patient perceived differences will be detectable and predictable between different MPK components within a certain individual allowing for the creation of the first ever clinical decision algorithm for MPK component selection.

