### **3. Study Procedures**

Upon recruitment and informed consent, participants will proceed through the following protocol steps until they have been fit with all 4 prosthetic devices in total.

*Randomization & Blinding:* The order with which each subject will be fit with an MPK will be randomized using a random number generator prior to enrollment. Subjects will not be blinded to device type as appearance of each device is a variable that may influence patient reported outcomes. Blinding of study personnel is not possible given that component-specific knowledge is required to tune each of the different MPKs. Data will be blinded for data analysis procedures to reduce any potential bias.

*Study procedures:*

1. Each device will be measured for length (overall build height) and weight prior to use in the study. Weight of devices will not be controlled due to anticipated effects on the outcomes and thus the final best selection.
2. Anthropomorphic data will be collected from each subject to include cause of amputation, K-level, waist circumference, leg length, residual limb length, build height between distal residual limb and knee center, weight, height, BMI, gender and age. These variables are unique characteristics associated with an individual which may have an impact on their successful use with one device over another. This data will only need to be collected once from each individual participant.
3. Subjects will be administered the Patient Scales of Preference and Importance survey to understand how they individually rank priorities with regards to their prosthetic care and aspects of their daily life. The AMPnoPro will be administered to the subject while they are not wearing their prosthesis to attempt simulation of a patient with a new amputation that has gone through physical therapy and ready for a definitive prosthesis. AMPnoPro has been shown to be predictive of the functional level of an amputee. [1]

Subjects will then undergo fitting and alignment of the prosthetic knees in a randomized order.

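### The 90% and 80% power printed for N=9 is omnibus four-knee power under the most favourable pattern of means; power to show the two-knee difference used for sizing is lower and is not given

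*Combined protocol and SAP*

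**What the plan says.** The analysis named for both aims is an omnibus test: "A repeated measures ANOVA with within factor MPK will be used to assess differences across treatment for Aims 1 and 2". Multiplicity is covered by one sentence, "Bonferroni-Holmes correction will be made to control for family-wise error rate", which does not say whether the family is the knee pairs, the endpoints or both.

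Each sizing effect is one difference divided by one SD. For Aim 1, "A Borg RPE of 2 (pooled SD= 2) was deemed clinically relevant for this study, resulting in an effect size of 1"; the gait variability index (GVI) uses 8/6, printed as 1.3. For Aim 2, OPUS uses 10/7.7 = 1.3 and PEQ uses 1.1/1.25 = 0.88. These values were converted to Cohen's f and entered in G*Power, "assuming a correlation among repeated measures of 0.5". The results are "These data indicate a sample size of approximately 9 will achieve 90% power" (Aim 1) and "The sample size of 9 corresponds to 80% power" (Aim 2).

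The section then proposes N=12, while the Specific Aims and section 2 give 17. Alpha, the number of measurements entered, the d-to-f formula and the assumed pattern of the four means are not printed. Nor is any power for a comparison of two knees.

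**The concern.** A Borg difference of 2 points or a PEQ difference of 1.1 points is most naturally read as a difference between one knee and another. The background section faults earlier work for grouping knees together "rather than teasing out differences between the individual MPK technology and what types of patients are best suited for each", so the trial's own question calls for knee-versus-knee comparisons. A significant omnibus F says only that the four means are not all equal.

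Since the power is printed directly after a two-knee difference, a reader can take 90% or 80% as the chance of showing that difference between two knees. A non-significant pair could then be reported as no difference, on the strength of power that the comparison did not have.

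**Working it through.** **Inputs.** Four knees, since participants continue "until they have been fit with all 4 prosthetic devices in total" (section 3), which gives six pairs. Correlation 0.5, Borg d=1, PEQ d=0.88, GVI and OPUS d=1.3 (Statistical & data analysis plan). Assumed because not printed: two-sided alpha 0.05, f=d/2, sphericity.

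**Step 1: reproduce the printed figures.** Repeated-measures omnibus F with m=4: lambda = f² × N × m / (1 − 0.5), on 3 and 3(N−1) degrees of freedom.
- Borg, f=0.50, N=9: lambda = 0.25 × 9 × 4 / 0.5 = 18; power 92.2% (N=8: 87.7%). The smallest N for 90% is 9.
- PEQ, f=0.44, N=9: lambda = 0.1936 × 9 × 4 / 0.5 = 13.9; power 83.4% (N=8: 77.4%). The smallest N for 80% is 9.
- The same calculation with three knees needs 11 (Borg, 90%) and 10 (PEQ, 80%); with two knees it needs 13 and 13. Of these, only the four-knee case returns both printed sample sizes.

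**Step 2: what f=d/2 implies.** f is the SD of the four means divided by the within-condition SD. For means (0, 0, d, d) it equals d/2, the largest value possible when the range is d. For means (0, d/2, d/2, d) the variance of the means is d²/8, so f = 0.354d. At N=9 lambda then falls to 9.0 (Borg) and 7.0 (PEQ), and omnibus power to 63.2% and 51.3%.

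**Step 3: power for one knee pair.** With correlation 0.5 the SD of a paired difference is SD × √(2 × 0.5) = SD, so the standardised paired difference equals d. The paired t-test has noncentrality d√N on N−1 degrees of freedom; at N=9 that is 3.00 (Borg) and 2.64 (PEQ). Holm over six pairs was simulated with compound symmetry under means (0,0,d,d), (0,d/2,d/2,d) and (0,0,0,d). Ranges are over these three patterns, for a pair that truly differs by d.

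| N | Test | Borg | PEQ |
|---|---|---|---|
| 9 | paired, uncorrected | 75% | 64% |
| 9 | paired, Holm | 40-45% | 30-33% |
| 9 | pooled ANOVA error, uncorrected | 82% | 72% |
| 9 | pooled ANOVA error, Holm | 56-61% | 43-47% |
| 12 | paired, uncorrected | 88% | 79% |
| 12 | paired, Holm | 62-68% | 48-53% |
| 17 | paired, uncorrected | 97% | 93% |
| 17 | paired, Holm | 86-90% | 73-79% |
| 17 | pooled ANOVA error, Holm | 91-94% | 81-85% |

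**Step 4: GVI and OPUS (d=1.3), N=9.** Paired power is 92.5% uncorrected, above the printed level. It is 66% at the first Holm step (0.05/6 = 0.0083), or 84% there with the pooled error. For these two measures the shortfall comes only from the correction.

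**The case against.** The strongest reply is that nothing has been miscalculated. The plan names a repeated measures ANOVA, converts d to f for it, and prints power that reproduces for that test. This stands: a reader might infer an arithmetic error, and the documents do not support that.

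Second, N=9 is a computed minimum, not the planned enrolment. This also stands in large part. At N=12 the uncorrected paired power (88% and 79%) is close to the printed 90% and 80%. At N=17 it exceeds them, and with Holm and the pooled error term it still meets them. It would be wrong to conclude that a 17-participant trial is badly underpowered. What remains is PEQ at N=17 with Holm and paired errors (73-79%), and both measures at N=12 with Holm, the N that the statistics section calls adequate even after attrition.

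Third, the lowest figures assume that Holm covers the six knee pairs. That is fair, but for Borg and PEQ, the two effects that fix N=9, a shortfall at that N is present before any correction.

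Finally, one might infer that non-significant pairs would feed the Aim 3 algorithm. The documents do not say so: Aim 3 is described as exploratory, with its model still to be chosen, and nothing links it to the outcome of pairwise group tests.

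**Conclusion.** The concern holds as a gap between the effect used for sizing and the test whose power is printed. The 90% and 80% at N=9 are omnibus power under the two-and-two pattern of means. For a pair of knees that differs by the sized amount, power at N=9 with paired errors is 75% (Borg) and 64% (PEQ) uncorrected, and about 40-45% and 30-33% with Holm over six pairs. The gap is moderate at N=12 and small at N=17, apart from PEQ under Holm with paired errors. For GVI and OPUS it appears only with correction.

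These figures rest on the plan's own SDs and its correlation of 0.5, and on an assumed two-sided alpha of 0.05, f=d/2, four measurements and no loss to follow-up. The exact match of both printed sample sizes supports the reading of the printed power, but it remains an inference.

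**What to change.** 1. In the Aim 1 and Aim 2 paragraphs, label the 90% and 80% as omnibus F power at N=9 with two knees at each extreme. Beside them, print knee-versus-knee power at the sample size settled on once 12 and 17 are reconciled. State alpha, the error term and the Holm family, and give both the paired and the pooled-error figures.

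2. For the six knee pairs, specify paired rather than pooled errors and replace Holm by Shaffer's step-down without an omnibus gate: compare the ordered p-values with 0.05/6, 0.05/3, 0.05/3, 0.05/3, 0.05/2 and 0.05/1. With four means, once one pair truly differs at most three others can be equal, so this never rejects less than Holm and needs neither sphericity nor a significant F. In simulation it added about 2-5 points of per-pair power at N=9 and 1-4 at N=17, with family-wise error at or below 5%. A version gated on the omnibus F, starting at 0.05/3, should not be used unless paired errors are specified: with pooled errors and one knee at three times the SD of the others, its family-wise error reached about 9%.

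3. Report every knee difference with a confidence interval, so that a non-significant pair is not read as equality.

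The cost is a change of SAP wording, with no added participants, visits or procedures. The stated power becomes less favourable. Paired errors also give up power when sphericity holds: from the Holm rows at N=17, about 4-5 points for Borg and 6-8 for PEQ, and more at smaller N.

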## **2. Participant population**

Subjects will be individuals with above the knee and below the hip amputation. This vulnerable population group will be protected through the use of safety equipment such as hand rails and a safety harness for the case of stumbles and falls. The goal is to collect data from at least 17 participants.

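### The sample-size section justifies N=12 although the trial sets 17; its only power figures are for N=9, and for Borg and PEQ they appear to rest on a favourable, unstated effect-size conversion

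*Combined protocol and SAP*

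**What the plan says.** Three sample sizes appear in the current text of the combined protocol and SAP.

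- **17.** The Specific Aims in section 1 plan to study three commercial knees and "one research grade powered knee in 17 individuals with TFA". Section 2 says: "The goal is to collect data from at least 17 participants".
- **12.** The Aim 1 part of the statistical plan says: "The sample size proposed in this study (N=12) should ensure adequate power, even in the event of attrition or slightly higher variability".
- **9.** The stated power figures are both for this size. For Aim 1: "These data indicate a sample size of approximately 9 will achieve 90% power". For the PEQ in Aim 2: "The sample size of 9 corresponds to 80% power".

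The test is an omnibus one: "A repeated measures ANOVA with within factor MPK will be used to assess differences across treatment for Aims 1 and 2". On the inputs the plan says: "Estimated effect size was calculated using Cohen's d for within factor designs [71], assuming a correlation among repeated measures of 0.5". It adds: "Effect sizes were then converted to Cohen's f for sample size estimations". It gives no f value, conversion formula, mean pattern over the four knees, alpha or attrition rate. The sources cited for this step are not in the reference list, which ends at number 6, so the conversion cannot be looked up.

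**The concern.** The section that should support the trial's size describes a different trial. A reader who wants the power at 17 finds no figure, and the reserve claimed for dropout and extra variability belongs to 12.

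The figures for 9 cannot be carried up to 12 or 17 either without knowing how d became f. A single standardised difference d between two of four knees does not fix f, because f also depends on where the other two knees lie. If the conversion was a favourable one, the margin at 12 is smaller than the text suggests, and the margin at 17 has to be worked out afresh.

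**Working it through.** **Inputs from the statistical plan**
- Borg: 2/2, d = 1.0.
- GVI: 8/6 = 1.33, stated as 1.3.
- OPUS: 10/7.7 = 1.30.
- PEQ: 1.1/1.25 = 0.88.
- Correlation among repeated measures 0.5; four knees (section 3).

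**Assumed, because not stated:** alpha 0.05 for the omnibus F test, sphericity, complete data, no multiplicity correction.

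**Formula.** Noncentral F with λ = f² × N × k/(1 − ρ). With k = 4 and ρ = 0.5, λ = 8 f² N, on 3 and 3(N − 1) degrees of freedom.

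**Step 1: reproduce the plan's figures.** Take f = d/2.
- Borg: f = 0.50, so λ = 8 × 0.25 × 9 = 18 and power is 92.2%. N=8 gives 87.7%, so 9 is the smallest N for 90%.
- PEQ: f = 0.44, so λ = 8 × 0.1936 × 9 = 13.9 and power is 83.4%. N=8 gives 77.4%, so 9 is the smallest N for 80%.

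Both N=9 statements are therefore matched exactly as minimum sample sizes.

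**Step 2: what f can be.** For four means whose largest difference is d:
- two extremes, two midway: f = √[(d²/4 + d²/4)/4] = d/√8 = 0.354d (the minimum);
- equally spaced: 0.373d;
- one knee differs from three equal ones: (√3/4)d = 0.433d;
- two knees at each extreme: d/2 = 0.5d (the maximum).

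**Step 3: power by pattern, Borg / PEQ, alpha 0.05**

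| Pattern | N=9 | N=12 | N=17 |
|---|---|---|---|
| Midway | 63% / 51% | 79% / 67% | 93% / 84% |
| Equally spaced | 68% / 56% | 83% / 72% | 95% / 88% |
| One differs | 82% / 70% | 93% / 85% | 99% / 96% |
| Two and two | 92% / 83% | 98% / 94% | 99.9% / 99% |

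GVI and OPUS (d = 1.3) depend far less on the pattern. Midway, the worst case, gives 87% at N=9, 96% at N=12 and 99.5% at N=17.

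**Step 4: another set of inputs that fits.** One knee differing with alpha 0.10 gives 90.1% / 81.6% at N=9 and 85.9% / 76.3% at N=8. Nine is again the minimum for both, so f = d/2 is not the only reading of the plan's figures.

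**Step 5: the reserve at 12 (Borg, alpha 0.05).** With one knee differing, power is 87.0% at 10 completers and 87.6% with the SD 10% higher. In the midway pattern it is 79.0% with nobody lost and 70.1% with the SD 10% higher.

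**Step 6: the reserve at 17 (midway pattern, Borg / PEQ, alpha 0.05)**
- 16 completers: 91% / 82%, both targets met.
- 15 completers: 89% / 79%, both narrowly missed.
- 17 completers, SD 10% higher (d = 1/1.1 = 0.909 and 0.88/1.1 = 0.80): 87% / 76%, both missed.

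**The case against.** The strongest reply is that no sum is wrong. The four d values follow from their inputs (GVI after rounding), and N=9 reproduces. That stands: this is an unreconciled sample size with an incompletely reported calculation. The favourable conversion is an inference. The authors may simply have used the ordinary two-mean conversion with no pattern in mind, and Step 4 shows a different fit. This is why the figures can only be said to appear to rest on it.

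A second reply is that the sentence on N=12 promises adequate power rather than 90%, and stands under Aim 1, before the PEQ is introduced. That also stands. Against the 80% that the plan accepts for the PEQ, Borg at N=12 without attrition falls short only in the midway pattern, by one point, and GVI is at about 96% or more throughout. A reader might infer that the assurance is false. The documents support only that, for Borg, it depends on the pattern.

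A third reply is that 17 is enough anyway. For the omnibus test with complete data, no shortfall is shown. But the plan does not say so, and Step 6 shows that its assurance about attrition and variability cannot be moved to 17 unchanged.

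**Conclusion.** The plan justifies 12 participants for a trial that sets 17, and gives power only for 9. This part is textual and needs no assumption. The second part rests on inferred inputs: at alpha 0.05 with sphericity, the N=9 figures for Borg and PEQ are reached only with the largest possible f; the other three patterns give 63–82% and 51–70%. The assurance about N=12 is pattern-dependent for Borg (79–98% with no attrition) and concerns a size that the trial does not use.

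Two stronger readings are tempting and not supported.
- **That the trial is underpowered.** At 17, omnibus power is 93–99.9% for Borg and 84–99% for the PEQ in every pattern (alpha 0.05, sphericity, no attrition, uncorrected). The plan intends a Holm correction but does not define its family, so there is no single corrected figure to set against these.
- **That comparisons between individual knees lack power for the PEQ.** A paired t test at 0.05/6 and N=17 would give 85% for Borg and 72% for the PEQ, but the six-pair family is an assumption. The plan names no pairwise contrast and states no pairwise power that could be contradicted.

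The matter should be fixed because the stated size is wrong as written. It does not threaten the planned omnibus analysis at 17.

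**What to change.** In the statistical plan:

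1. Replace 12 with 17, and say whether 17 means enrolled or completing.
2. Replace the N=9 statements with power at 17. State alpha, the conversion from d to f, and either one justified mean pattern or the range from d/√8 to d/2. At alpha 0.05, with sphericity, no attrition and no correction, the range is 93–99.9% for Borg and 84–99% for the PEQ.
3. Restate the sentence on attrition and variability for 17. In the least favourable pattern, 16 completers still meet both targets (91% / 82%), while 15 completers (89% / 79%) or an SD 10% higher (87% / 76%) narrowly miss them.

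The cost is a short recalculation and a few sentences of text. Enrolment stays at 17, and neither the design nor the planned test changes.
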